6.1 Full Analysis Set

Full Analysis Set defined as all subjects that are enrolled and receive at least 1 dose of AMG 397. The analysis of all endpoints, unless noted otherwise, will be conducted on the Full Analysis Set.

6.2 DLT Evaluable Analysis Set

A subject is deemed DLT evaluable if during the DLT-observation period the subject met at least one of the following criteria:

- received at least 75% of the planned dose of AMG 397
 - in Parts 3A/3B: and received at least 85% of the planned dose of azacitidine
 - in Part 3C: and received at least 75% of the planned dose of dexamethasone
- experienced a DLT

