**Table 3. Planned Doses per Dose Cohort Level**

Dose Cohort Levels	Dose (mg) PO
1	80
2	160
3	320
4	640

Dose escalation for Group 1A and Group 1B will begin with 2-4 subjects treated at the lowest planned dose level of 80 mg. Dose escalation will follow the planned schedule described above with 2-4 subjects treated in each cohort.

DLRT will convene to review the safety data and determine the appropriate dose to be implemented. Dose escalation/de-escalation decisions will be guided by the BLRM model of dose toxicity. Skipping of planned dose levels is not allowed. Dose escalation decisions will not be made until all subjects in a cohort(s) are monitored through the DLT-observation period of 28 days following treatment initiation. Intermediate dose levels and alternative dosing schedule(s) may be explored based on emerging pharmacokinetic and safety data per the decision of the DLRT.

Dose escalation for both Group 1A and 1B respectively, will continue until any of the following events:

- The highest planned dose level for each group is determined to be safe and tolerable (minimum of 6 evaluable subjects)
- MTDs are identified for each group where BLRM repeats the recommendation of a dose level (minimum of 6 evaluable subjects)
- The maximum of 30 evaluable subjects have been enrolled in each group. If fewer than 6 subjects are treated at the MTD/RP2D, additional subjects may be enrolled to confirm safety and tolerability.

Intermediate doses and alternative dosing schedule(s) may be explored based on emerging pharmacokinetic and safety data as decided by the DLRT.

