### **3.4 Replacement of Subjects**

During dose escalation, subject(s) may be replaced if:

- Subject(s) is not DLT-evaluable. See [Section 6.2.1.2](#) for definition of DLT-evaluable
- Subject(s) discontinues treatment for any reason other than a DLT during the DLT-observation period

Additional subjects may also be enrolled if Amgen’s medical monitor determines that the minimum required number(s) of evaluable subjects have not been enrolled in each cohort.

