#### **6.2.1.2 Dose-cohort Study Escalation and Stopping Rules**

The Dose Level Review Team (DLRT) will convene before decisions to dose escalate or de-escalate is made or when cohorts are suspended per protocol. The DLRT will be composed of select Investigator(s), Amgen medical monitor, Amgen Global Safety Officer or designee, Amgen Clinical Research Study Manager (CRSM) and Biostatistics representative or designee. Additional members may be added as needed (eg, clinical pharmacologist). The DLRT voting members include the Amgen Medical Monitor and Global Safety Officer or designee, in consultation with the investigator(s) or designee. The DLRT members are responsible for dosing decisions, which may include escalation to the next nominal or intermediate dose, de-escalation to a lower nominal or intermediate dose; alternative dose frequencies, continuation, delay or termination of dosing; or repetition or expansion of a cohort; implementation of lead-in dosing, or determination of RP2D. See [Section 3.1](#) for more details regarding the study design and the dose escalation plan for this study.

The DLT-observation period is defined as, at minimum, 28 days after the initial dose of AMG 397. Once lead-in dosing period is initiated, the DLT-observation period is defined as the amount of time for subject(s) for each dose cohort to receive at least 1 week of lead-in dose and 3 weeks of target dose.

A subject is deemed DLT-evaluable if during the DLT-observation period the subject met at least one of the following criteria:

- Received at least 75% of the planned dose of AMG 397
- Experienced a DLT

Available study data, including data collected after the initial DLT-observation period along with demographics, IP administration, medical history, concomitant medications,

adverse events (AE), ECG, vital signs, laboratory results and PK/PD information will be reviewed. In addition to DLTs, all  $\geq$  grade 3 toxicities not meeting DLT criteria will be reviewed and may be considered in DLRT decisions. Modeling of available potential safety risk data (eg, for thrombocytopenia) to predict safety risk for dose escalation decisions may also be considered.

Dose escalation/de-escalation decisions will be guided by the BLRM model of dose toxicity described by [Appendix D](#). An Amgen representative will notify the sites in writing the dosing decision from the DLRM and when a cohort is open to screen new subjects.

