- **IMWG-URC for MM**
- **2017 ELN criteria for AML**
- **Revised IWG for MDS**
- **Lugano Classification for NHL**

Dose Limiting Toxicity (DLT)

Unless otherwise specified, investigators determine whether an adverse event qualifies as a DLT per the definition described in the protocol.

DLT Observation Period

The DLT observation period is defined as, at minimum, 28 days after the initial dose of AMG 397. If lead-in dosing period is initiated, the DLT-observation period is defined as the amount of time for subject(s) for each dose cohort to receive at least 1 week of lead-in dose and 3 weeks of target dose.

Duration of Response (DOR)

Duration of response is calculated for subjects who have achieved response (PR or better). It is defined as time from the first observation indicating a response to the subsequent date of disease progression or death, whichever is earlier.

DOR time in months: (date of disease progression or death - date of the first observation of response +1)/30.4

Subjects without disease progression or death until the analysis data cut-off date will be censored at the last adequate disease assessment date.

Fridericia-corrected QT Interval (QTcF)

The Fridericia correction will be calculated from the investigator reported QT (msec) and RR interval (msec): $QTcF = QT / (RR/1000)^{1/3}$

Investigational Product (IP)

IP is used in reference to AMG 397.

Overall Response Rate (ORR)

ORR is the incidence of either PR or better based on investigator assessment. All subjects that do not meet the criteria for response (PR or better) by the analysis cutoff date will be considered as non-responders.

Progression-free survival (PFS)

PFS time is calculated as time from first dose of IP date to disease progression date or death due to any cause, whichever is earlier.

PFS time in months: (date of disease progression or death - first dose of IP date +1)/30.4

Subjects without disease progression or death until the analysis data cut-off date will be censored at the last adequate disease assessment date. If no post-baseline disease assessment, censoring is at the first dose of IP date.

Overall survival (OS)

OS is defined as the time from first dose of IP date until death due to any cause.

OS time in months: (date of death - first dose of IP date +1)/30.4

Patients without event will be censored at their last date known to be alive.

Study Day

Post study day 1: study day = (date –Study Day 1) + 1

Pre study day 1: study day = (date –Study Day 1)

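### A DLT-free subject counts as DLT-evaluable on dose share alone, so one who leaves observation after about day 15 or 16 enters the dose decision as a full non-event

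*SAP*

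**What the plan says.** SAP Section 6.2 offers two alternative routes into the DLT Evaluable Analysis Set: "A subject is deemed DLT evaluable if during the DLT-observation period the subject met at least one of the following criteria". One is "received at least 75% of the planned dose of AMG 397"; the other is "experienced a DLT". Part 3 adds a partner-drug share to the first route, for example "in Parts 3A/3B: and received at least 85% of the planned dose of azacitidine". Protocol Section 6.2.1.2 has the same rule for monotherapy: "Received at least 75% of the planned dose of AMG 397", or a DLT.

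The window is set in SAP Section 5: "The DLT observation period is defined as, at minimum, 28 days after the initial dose of AMG 397". With a lead-in it becomes the time needed for at least one lead-in week and three weeks at target dose.

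The evaluable count is the number of subjects with which SAP Table 1 is entered (Section 3.3). It is also the analysis set for the DLT incidence table (Section 9.6.1), and DLT incidence is a primary endpoint.

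Two protocol provisions come close to this point. Section 3.1 holds escalation decisions "until all subjects in a cohort(s) are monitored through the DLT-observation period of 28 days following treatment initiation". Section 3.4 allows replacement of a subject who is not DLT-evaluable and, as a separate ground, where "Subject(s) discontinues treatment for any reason other than a DLT during the DLT-observation period". Replacement is optional.

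**The concern.** The 28-day window limits when doses and DLTs are counted. It does not say how long a subject must be watched. A subject with no DLT becomes evaluable on the day the dose share reaches 75%, whatever happens next. If that subject then dies of progression, withdraws consent or is lost, the rest of the window is unobserved, yet the subject is entered as if it had been clean.

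The error runs one way: the observed DLT rate is biased down and dose decisions lean towards escalation. Cohorts start with 2 to 4 subjects in Parts 2A and 2C and 3 to 4 in Part 3, so one subject can matter. DLTs that need persistence are the easiest to miss, such as grade 4 neutropenia lasting more than 7 days in the MM and NHL criteria of protocol Section 6.4. Early exit is plausible in a relapsed or refractory population where entry asks for an expected survival of more than 3 months, although neither document gives its frequency.

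**Working it through.** **When the threshold is reached.** Protocol Section 2.3.1.1 gives 8 administrations per 28-day cycle on the twice-weekly schedule. Two days × 4 weeks = 8, which reproduces that figure; the dosing days are 1, 2, 8, 9, 15, 16, 22 and 23. The SAP says only that Parts 2 and 3 are dosed weekly, so days 1, 8, 15 and 22 are an assumption.

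- Twice weekly: 0.75 × 8 = 6 doses, reached on day 16; 28 − 16 = 12 days remain (12/28 = 43%).
- Weekly: 0.75 × 4 = 3 doses, reached on day 15; 28 − 15 = 13 days remain (13/28 = 46%).

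A lower lead-in dose moves this later if planned dose is counted in mg. With 80 mg then 120 mg twice weekly, the total is 2 × 80 + 6 × 120 = 880 mg and 75% is 660 mg. By day 16 the subject has had 160 + 480 = 640 mg, so the threshold falls on day 22 and 6 days remain. Weekly dosing also gives day 22: 320 of 440 mg by day 15, against 330 needed. In Part 3 the partner-drug share must be met too, and those dosing days are not in the documents supplied.

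**Effect on SAP Table 1.** Taking the table as given, compare each cell with x DLTs in n − 1 subjects with the cell for x in n, the added subject being an unobserved DLT-free leaver. The decision changes in four cells:

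| Leaver not counted | Leaver counted |
|---|---|
| 1/2 De-escalate | 1/3 Stay |
| 1/5 Stay | 1/6 Escalate |
| 2/6 De-escalate | 2/7 Stay |
| 3/9 De-escalate | 3/10 Stay |

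Every change is towards less caution. With zero DLTs there is none: 0/1, 0/2 and 0/3 all read Escalate.

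**What is lost with zero DLTs.** Let p be the true 28-day DLT risk and q the risk observable by day 15. Under a constant hazard, q = 1 − (1 − p)^(15/28). For p = 0.33, q = 0.19; for p = 0.25, q = 0.14. The chance of 0/3 is (1 − p)³ with full observation, (1 − p)²(1 − q) with one leaver and (1 − p)(1 − q)² with two.

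| True risk | None leave | One leaves | Two leave |
|---|---|---|---|
| 0.33 | 30% | 36% | 44% |
| 0.25 | 42% | 48% | 55% |

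Uniform onset over 28 days (q = 15p/28) gives 37% and 45% at 0.33, and 49% and 56% at 0.25. Onset concentrated earlier shrinks the effect; later onset enlarges it. Excluding the leaver does not undo these increases, because 0/2 and 0/1 still read Escalate. Only a fully observed replacement does.

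**The case against.** The best defence is that stopping drug does not end observation. Protocol Section 8.1 asks that subjects who discontinue stay on study. Section 9.2.1.1 collects adverse events through the safety follow-up or end-of-study visit, and Section 7.4.4 places safety follow-up 28 (+7) days after the last dose. A reader might infer that anyone who stops drug or starts another therapy after day 16 goes unobserved. The documents do not support that: such subjects remain followed, and after a switch the data are confounded rather than absent. For MM and NHL, a treatment-related grade 5 event not clearly due to progression is itself a DLT. The gap is therefore confined to progression deaths, consent withdrawals and losses.

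A reader might also infer that protocol Sections 3.1 and 3.4 contradict the evaluability rule. They do not. Section 3.1 governs when a decision is taken, and Section 3.4 gives optional grounds for replacement; a subject can be both evaluable and replaceable without inconsistency. They are partial safeguards. But neither says how a subject who cannot be monitored to day 28 is classified, and neither takes a replaced subject out of the denominator.

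The dose level review team also sees all safety data, Table 1 is a guideline, and a single related grade 3 troponin elevation forces de-escalation regardless. This softens the consequence but does not correct the count.

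**Conclusion.** The point stands for subjects who leave observation without a DLT after meeting the dose share. They are counted as complete non-events with up to 12 (twice weekly) or 13 (weekly) of 28 days unobserved, and fewer where a lead-in or partner-drug condition delays the threshold. One such subject makes Table 1 less cautious in four cells.

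The rise in the chance of 0/3 should not be read as something a new definition alone would reverse. It rests on an assumed onset pattern, two leavers out of three is an extreme case, and the benefit there comes only through replacement, which Section 3.4 already permits.

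Part 1, which used the BLRM, is closed to enrolment, so the live decisions are those made with Table 1 in Parts 2A, 2C and 3. The protocol supplied is Amendment 1, whereas the SAP is written to Amendment 4. The protocol text for Parts 2 and 3, including any follow-up condition, could not be checked. The SAP's own definition contains none. The change is worth making because the bias is anti-conservative and cheap to remove.

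**What to change.** In SAP Section 6.2 and the matching protocol text, require that a subject without a DLT both received the stated dose share and was followed for DLTs through the end of the DLT-observation period. Keep a DLT as the alternative route. State that subjects lost earlier without a DLT are excluded from the Table 1 denominator and may be replaced under the existing rule. Leave the other replacement grounds in protocol Section 3.4 as they are; making evaluable and replaceable mutually exclusive would remove useful flexibility. Flag subjects who start new anticancer therapy within the window for dose level review team consideration rather than excluding them automatically. Check the Amendment 4 wording for Parts 2 and 3 and align it.

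The cost is a clause or two in each document, and an occasional early leaver who becomes non-evaluable and may need replacing.

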6.3 Pharmacokinetic Analysis Set

The PK Analysis Set will contain all subjects who have received at least 1 dose of AMG 397 and have at least 1 PK sample collected. These subjects will be evaluated for PK analysis unless the number of data points required for analysis is not enough, or

significant protocol deviations have affected the data, or if key dosing or sampling information is missing.

7. Planned Analyses

The planned analyses are described in following sections.

7.1 Interim Analysis and Early Stopping Guidelines

No formal interim efficacy analysis is planned. Safety data will be reviewed on an ongoing basis. Interim safety analyses will be performed for each dose level of each cohort to support the evaluation of safety by the DLRT. After reviewing all available safety data and reviewing the dose recommendation from mTPI, the DLRT will make all dose level and dosing schedule decisions.

Upon the completion of each cohort or each part, interim analyses can be performed to evaluate safety and efficacy data.

7.2 Primary Analysis

The primary analysis will occur when target enrollment is complete and each subject either completes 6 months on study or withdraws from the study.

7.3 Final Analysis

The final analysis will occur after all subjects have ended the study.

8. Data Screening and Acceptance

8.1 General Principles

The objective of the data screening is to assess the quantity, quality, and statistical characteristics of the data relative to the requirements of the planned analyses.

8.2 Data Handling and Electronic Transfer of Data

The Amgen Global Study Operations-Data Management (GSO-DM) department will provide all data to be used in the planned analyses. This study will use the RAVE database.

8.3 Handling of Missing and Incomplete Data

The following imputation of missing values will be done:

Incomplete adverse event, concomitant medication dates and dates used for the derivation of time to efficacy endpoints will be imputed as per [Appendix A](#).

Non-pharmacokinetic measurements that are above or below the quantification limits will be considered equal to the upper or lower limit of quantification for all analyses unless explicitly noted otherwise.

8.4 Detection of Bias

Lack of protocol compliance and the potential for biased statistical analyses will be examined by listing important protocol violations by cohort and site.

8.5 Outliers

Outlier data will not be excluded unless scientifically justified.

Pharmacokinetic (PK) concentration data will be evaluated for outliers by visual inspection, and decisions to re-assay individual samples will be made in accordance with standard pharmacokinetic evaluation practice.

8.6 Distributional Characteristics

Where appropriate, the assumptions underlying the proposed statistical methodologies will be assessed. If required data transformations or alternative non-parametric methods of analyses will be utilized.

8.7 Validation of Statistical Analyses

Programs will be developed and maintained, and output will be verified in accordance with current risk-based quality control procedures.

Tables, figures, and listings will be produced with validated standard macro programs where standard macros can produce the specified outputs.

The production environment for statistical analyses consists of Amgen-supported versions of statistical analysis software; for example, the SAS System version 9.4 or later.

9. Statistical Methods of Analysis

9.1 General Considerations

Descriptive statistics on continuous data will include means, medians, standard deviations and ranges, while categorical data will be summarized using frequency counts and percentages. Graphical summaries of the data may also be presented. When data are summarized by time, the values recorded against the scheduled time points listed in the protocol will be used. When assessing minimum/maximum increases or decreases over the study, all assessments, including unscheduled assessments will be used.

For each indication, efficacy and safety data will be summarized by dose level.

For the subjects who complete the DLT period and proceed to a higher dose level or crossover to a combinational therapy cohort for the following treatment cycle,

efficacy and safety data will be summarized per their initial assigned dose level.

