3.1 Study Design

This is a first-in-human (FIH), multicenter, non-randomized, open-label, phase 1 study evaluating AMG 397 administered orally in adult subjects with selected RR hematological malignancies.

Part 1 of the study was designed to investigate AMG 397 as monotherapy on a twice weekly dosing schedule (ie, once daily for 2 consecutive days followed by 5 days break at a weekly interval [QD2]) in subjects with MM, NHL, and AML (Figure 1). In July 2019, reports of troponin elevations occurring at the highest dose level investigated of

320 mg/m² resulted in the clinical trial being placed on hold. In 2020, the study was redesigned to investigate low weekly doses of AMG 397 including Part 2 ([Figure 2](#), [Figure 3](#)) and Part 3 ([Figure 2](#)) as follows:

- Parts 2A will enroll subjects with MDS or AML (monotherapy [QW]) for dose escalation and subjects with only MDS for dose expansion
- Parts 2B will enroll subjects with AML in Japan (monotherapy [QW])
- Parts 2C will enroll subjects with 1q21 amp MM (monotherapy [QW])
- Parts 3A will enroll subjects with MDS (AMG 397 + azacitidine) for dose escalation and dose expansion
- Parts 3B will enroll subjects with AML (AMG 397 + azacitidine) for dose escalation and dose expansion
- Parts 3C will enroll subjects with 1q21 amp MM (AMG 397 + dexamethasone) for dose escalation and dose expansion

Study Design and Treatment Schema

Figure 1. Part 1 Study Design and Treatment Schema (CLOSED TO ENROLLMENT)

[figure not shown]

Figure 2. Parts 2A, 2C, and 3 Study Design and Treatment Schema (Dose Escalation and Dose Expansion)

[figure not shown]
[figure not shown]

Figure 3. Part 2B Study Design and Treatment Schema (AML Subjects in Japan)

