At least 6 evaluable subjects need to be treated at the dose level of MTCD.

Guidelines for dose level decisions can be found in [Table 1](#). Please note one exception to the guidelines provided in [Table 1](#), a single grade 3 treatment related troponin elevation will result in dose de-escalation regardless of number of subjects treated at current dose.

Table 1. Guidelines for Dose Level Decisions for Parts 2A and 2C and Part 3

No. of DLT-evaluable ^a subjects treated at current dose	Number of DLTs		
	Escalate	Stay at current dose	De-escalate ^b
1	0	-	1
2	0	-	≥ 1
3	0	1	≥ 2
4	0	1	≥ 2
5	0	1	≥ 2
6	0-1	-	≥ 2
7	0-1	2	≥ 3
8	0-1	2	≥ 3
9	0-1	2	≥ 3
10 ^c	0-1	2-3	≥ 4

DLT = dose-limiting toxicity.

^a See Section 6 for definition of DLT evaluable.

^b De-escalate guideline applies only when current dose level and enrollment is allowed to a lower dose level.

^c The maximum number of evaluable subjects at one dose level is 10.

The MTCD is defined as the highest dose with a probability of DLT lower than or close to a targeted toxicity probability of 0.2.

4. Covariates and Subgroups

There are no planned covariates in this study.

If appropriate the following baseline variables may be used to evaluate efficacy endpoints in subgroup analysis: Age at baseline (< 65, ≥ 65), sex, race, prior lines of anti-cancer therapy (1, 2, >2).

5. Definitions

Age at Enrollment

Subject age at enrollment will be determined using the age in years reported in the clinical database.

Baseline

Unless otherwise specified, baseline will be defined as the last assessment before the first dose of investigational product (AMG 397).

Baseline and Post-Baseline Electrocardiogram (ECG) Values in Triplicate

For the three baseline triplicate ECG, the mean of values in a triplicate should be calculated before taking the mean of the three baseline averages.

For all post-baseline ECG, the mean value for measurements taken at the same assessment will be calculated and used in the analysis.

When an ECG is missing within a triplicate, all available data within that assessment visit will be averaged for that time point.

Bazett-corrected QT Interval (QTcB)

The Bazett correction will be calculated from the investigator reported QT (msec) and RR interval (msec): $QTcB = QT / (RR / 1000)^{1/2}$

Best Overall Response (BOR)

Best overall response for a subject is the best observed post-baseline disease response based on investigator assessment. Response criteria are as follows:

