
Study Day 1

Study day 1 is defined as the first day of administration of the investigational product after enrollment. The day prior to Study Day 1 is considered Day -1.

Treatment-Emergent Adverse Event (TEAE)

A treatment-emergent adverse event is any adverse event starting on or after the first dose of investigational product, as determined by "Did event start before first dose of investigational product" equal to "No" or missing on the Events eCRF, and up to and including 30 days after the last dose of investigational product excluding events reported after end of study date.

Time to Response (TTR)

Time to response is defined as the time from the first dose of IP until the first documentation of objective response. Only subjects who have achieved objective response will be evaluated for TTR.

TTR time in months: (date of the first observation of response - first dose of IP date +1)/30.4

6. Analysis Sets

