9.6 Safety Analyses

9.6.1 Adverse Events

The Medical Dictionary for Regulatory Activities (MedDRA) version **23.1** or later will be used to code all events categorized as adverse events to a system organ class and a preferred term. The severity of each adverse event will be graded using (CTCAE) version 4.03 ([Appendix C](#)).

Subject incidence of all treatment-emergent adverse events, serious adverse events, grade 3 or higher, treatment-related, serious treatment-related, adverse events leading to withdrawal of investigational product, and fatal adverse events will be tabulated by system organ class and preferred term by dose level.

Subject incidence of DLTs will be summarized by dose level and preferred term using the DLT Evaluable Analysis Set.

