9.6.2 Laboratory Test Results

The analyses of safety laboratory data will include summary statistics at the scheduled time points by dose cohort. Shifts in CTCAE grades of safety laboratory parameters between baseline and the worst post-baseline value for select blood chemistry analytes (creatinine, total bilirubin, aspartate aminotransferase [AST], alanine aminotransferase [ALT], and alkaline phosphatase [ALP]) and hematology analytes (hemoglobin, platelet count, total neutrophils) will be tabulated by dose cohort.

A summary of potential hepatotoxicity by Hy's Law will be tabulated. The criteria are defined as AST or ALT > 3 times upper limit of normal (ULN), total bilirubin \geq 2 times ULN, and ALP < 2 times ULN for baseline and on study assessed within 7 days.

Subject incidence of troponin elevation will be summarized.

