9.6.7 Exposure to Investigational Product

Descriptive statistics will be produced to describe the exposure to AMG 397 by dosing schedule. Number of cycles initiated, number of doses, duration of treatment, average dose delivered per day, average dose delivered per treated week and cumulative dose will be summarized. Subject incidence of dose modification along with the reason for dose modification will be summarized.

A listing of the unique manufacturing lot numbers, and a listing of the subjects administered each manufacturing lot number will be provided.

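### Subjects who escalate or cross over to combination therapy are reported wholly under their starting dose, so post-switch events and responses appear as outcomes of that dose

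*SAP*

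**What the plan says.** SAP Section 9.1 makes dose level within indication the unit of reporting for efficacy and safety. It then deals with subjects who finish the DLT period and "proceed to a higher dose level or crossover to a combinational therapy cohort for the following treatment cycle": for them, "efficacy and safety data will be summarized per their initial assigned dose level". Protocol Section 3.1 (Intra-subject Dose Escalation) permits the escalation. The supplied protocol has no combination part, but the SAP wording itself provides for crossover.

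The definitions and tables to which this rule applies are:

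- **Treatment-emergent adverse events** (SAP Section 5) are counted "up to and including 30 days after the last dose of investigational product excluding events reported after end of study date".
- **Best overall response** (SAP Section 5): "Best overall response for a subject is the best observed post-baseline disease response based on investigator assessment".
- **Adverse event tables** (SAP Section 9.6.1): the listed categories through "fatal adverse events will be tabulated by system organ class and preferred term by dose level".
- **Laboratory data** (SAP Section 9.6.2): grade shifts run from baseline to the worst later value, and "Subject incidence of troponin elevation will be summarized".
- **Exposure** (SAP Section 9.6.7): "Descriptive statistics will be produced to describe the exposure to AMG 397 by dosing schedule".

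**The concern.** By-dose safety and response tables are a main product of a non-randomized dose-finding study. SAP Section 3.1 says the trial was put on hold after "reports of troponin elevations occurring at the highest dose level investigated of" 320 mg/m², so the dose at which a troponin elevation arises is central to reading the results. Under Section 9.1, an elevation first seen after a subject has moved up is counted against the lower starting dose. For a crossover subject, the row mixes AMG 397 alone with AMG 397 plus azacitidine or dexamethasone, although SAP Section 2.1 sets separate monotherapy and combination efficacy objectives. A reader of that row cannot separate outcomes before the switch from those after it.

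Switchers are absent from both the numerator and the denominator of the later-dose or combination row, so no bias is claimed there.

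**Working it through.** **Does anything in the SAP cut the data at the switch?** The plan states no figure to reproduce, so the first step is to read the rule against each definition.

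- Treatment-emergent adverse events close 30 days after the last AMG 397 dose at any level, not at the switch.
- Best overall response and ORR have no cut at the switch; ORR runs to the analysis cutoff.
- PFS and DOR are censored at the last adequate disease assessment, with no provision for escalation or crossover.
- Laboratory shifts use the worst post-baseline value. Maximum QTc change uses all assessments, including unscheduled ones.
- Exposure is summarized by dosing schedule, so it does not show how much of a row's exposure was at a later dose.

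The answer is no. That the initial-dose summary is the only one is an inference: the SAP does not say so, but it names no other.

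**How far can a row move?** From SAP Section 3.3, cohorts start at 2–4 subjects (3–4 in Part 3), with up to 10 at the highest level or MTD/MTCD. One post-switch event moves the displayed rate by 1/n: 50 points at n = 2, 25 at n = 4 and 10 at n = 10.

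**Illustration for adverse events.** All inputs are assumed: a row of 6, four cycles, switch after cycle 1, per-cycle risk p before the switch and q after it, and k switchers.

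- Stays: 1 − (1 − p)^4. With p = 5%: 1 − 0.95^4 = 0.1855.
- Switches: 1 − (1 − p)(1 − q)^3. With q = 25%: 1 − 0.95 × 0.75^3 = 0.5992.
- Row shown: [(6 − k) × stays + k × switches] / 6.

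| p / q | k | Row shown | If all had stayed |
|---|---|---|---|
| 5% / 25% | 1 | 25.4% | 18.6% |
| 5% / 25% | 2 | 32.3% | 18.6% |
| 5% / 25% | 3 | 39.2% | 18.6% |
| 5% / 15% | 2 | 26.3% (switcher 0.4166) | 18.6% |
| 10% / 20% | 2 | 40.9% (stays 0.3439, switcher 0.5392) | 34.4% |

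**The same data by dose at onset** (5% / 25%, k = 2):

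- Starting dose: (4 × 0.1855 + 2 × 0.05) / 6 = 0.842 / 6 = 14.0%, over 4 × 4 + 2 × 1 = 18 subject-cycles.
- Later dose: 1 − 0.75^3 = 57.8% of two subjects, over 2 × 3 = 6 subject-cycles.
- Per subject-cycle: 0.842 / 18 = 4.7% against (2 × 0.578) / 6 = 19.3%. The initial-dose row hides this contrast.

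**Illustration for ORR** (assumed): 5% respond on monotherapy, 20% of non-responders cross over, and a fraction r of those respond. The monotherapy row shows 0.05 + 0.95 × 0.20 × r, which is 6.9%, 8.8% and 10.7% for r = 10%, 20% and 30%.

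**The case against.** Summarizing by initial assignment is a recognized convention. It keeps each subject in one row, keeps escalators selected for having had no DLT out of higher-dose rows, and leans towards over-reporting toxicity at lower doses. The analysis is descriptive, with no hypothesis test. The DLRT reviews all available safety data, and the troponin de-escalation rule in SAP Section 3.3 works at the current dose whatever Section 9.1 says. All of this stands. It is the reason to keep the initial-dose table and to limit the point to reporting.

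Other planned outputs recover part of the information:

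- QTcF against AMG 397 concentration (SAP Section 9.6.5) reflects actual exposure, but covers only QTcF.
- Cumulative dose, average dose, dose modifications, and azacitidine and dexamethasone exposure are summarized (SAP Sections 9.6.7 and 9.6.8), but totals do not date events.
- Subject-level data are provided for time-to-event endpoints (SAP Section 9.5), not for adverse events or laboratory values.
- Exposure-response work is deferred to a supplemental plan.

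None of these assigns adverse events, troponin elevations or responses to the dose or regimen received.

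Two cautions also stand. The SAP follows protocol Amendment 4, which was not supplied, so the timing and frequency of crossover are unknown. The magnitudes are assumed, and small rows are imprecise in any case: the exact 95% interval for 2 of 6 is 4% to 78%. That imprecision does not excuse placing an event under a dose the subject was no longer taking. Finally, crude incidence by dose at onset is lowered by shortened follow-up (14% above, against 19% had all stayed), so exposure time must stand beside it.

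**Conclusion.** The point holds and should be fixed. It follows from an explicit SAP rule combined with definitions that do not stop at the switch. Following the SAP will place post-switch adverse events, laboratory and ECG changes, and responses in the starting-dose row.

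In the assumed six-subject examples, the distortion is about 7 points under the milder risks with two switchers, and about 7 to 21 points under 5% / 25% with one to three. The monotherapy ORR of 5% becomes 7% to 11%. The actual size cannot be determined without the number of switchers and the true risks. For crossover subjects it also depends on the Amendment 4 rules.

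**What to change.** Keep the initial-dose summary in SAP Section 9.1 and add:

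1. Adverse event, laboratory (including troponin) and ECG tables by dose and regimen received at onset, with subject-cycles of exposure in each column.
2. ORR and best overall response by initial dose level, counting only responses first documented before the switch. Flag responses after escalation and after crossover and report them separately.
3. The number of switchers in each initial-dose row.
4. If Amendment 4 allows crossover before progression, a sensitivity analysis of PFS and DOR cut at the first combination dose, noting that such censoring may be informative.

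The cost is SAP wording and one derivation from dosing dates already collected; conduct and dosing do not change. Some subjects will appear in more than one safety column. Later-dose columns will contain escalators selected for having had no DLT and will carry later-cycle exposure. The tables should state both limits.
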